These individuals will not be concurrently enrolled in any other experimental studies unless approved by the principal investigator. Each research participant will be given a coded identification number to designate all evaluations. We will retain the data for reporting to granting agencies even when the individual is not eligible for the study. This data will be stored by the coded identification number without information identifying the individual.

We will evaluate the research participants for: 1) functional neurophysiological assessment (FNPA); 2) somatosensory evoked potentials (SEP); 3) sympathetic skin responses (SSR); 4) efferent motor activity during standing; 5) efferent motor activity during stepping; 6) reflexes during supine, prone, sitting and standing; 7) bladder function; and 8) cardiovascular function. Each of these measurements will take between 1 and 4 hours. The FNPA, SEP and SSR will be performed while the research participant is lying supine on a mat. The efferent motor assessments will be performed in the body weight support treadmill with the assistance of trainers at the hip and at each leg.

We will assess metabolic parameters, inflammatory markers, complete blood count, bone density and health markers, blood glucose control and drug toxicity panel. A trained

technician will draw a venous blood sample. Participants may undergo a 12-hour fast the night before, including no food or drink including alcohol or caffeine (water is permitted). A comprehensive drug screen by urinalysis will be done to assess the use of illicit drugs. These blood and urine analyses may be repeated periodically throughout the course of the study. A blood sample will be stored for batch processing at the end of the study (for participants that complete the screening process).

After completion of these evaluations, participants will undergo 80 sessions of step/stand training. We will repeat experiments after the completion of the 80 training sessions to quantify that no motor pattern changes are achievable with locomotor training alone. Drs. [name], [name] and [name] will meet to discuss the results of the preliminary testing and evaluate if the participant is eligible for surgical implantation for SCES.

FULL ENROLLMENT: Surgery + Epidural Stimulation + Training (2nd consent)

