Locomotor Training: Every research participant will be slowly acclimated to the body weight support system to make him/her feel comfortable in an upright position. This may help the research participant avoid experiencing a lowered blood pressure or dizziness. However, if these conditions should occur, the research participant would immediately be

unhooked from the system, removed from an upright position, the legs elevated, and the blood pressure monitored. Stepping bouts are relatively short in duration, thus an increase in respiration as well as an increase in heart rate or blood pressure will generally last for only a couple of minutes. Each research participant will be closely monitored through each experiment and training session. Standing or stepping will immediately halt once the research participant feels tired or winded. Blood pressures and heart rates will be monitored by the physical therapist or trained staff regularly during each training session. Continuous blood pressure, breathing rate, and temperature may be monitored with sensors throughout the training sessions and experiments. Participants may be asked to train twice a day; they will train both to stand and step on the same day. The sessions will only be counted if the progression criteria is met, for example independence minutes or weight-bearing minutes.

In certain cases, the physician, [name], might recommend a specific training change or limit on sessions to mitigate risk for research participant. Any special considerations are specified in the addendum section.

Before and after every experiment and training session, a physical therapist or research staff member will examine the research participant's skin for irritations and abrasions. If skin irritations or abrasions are caused by the electrodes, harness position or hand placements of trainers, electrode, the harness and hand placement will be modified appropriately. Further, the physical therapist and research team will constantly monitor the research participant's skin and muscle for signs of muscle strain, joint sprain and skin irritation (e.g. temperature and redness).

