[name] and the research team will continually assess the appropriate BWS and continuously monitor manual assistance by trainers to avoid joint sprain and fracture. Body weight support will be kept above 50% for the initial sessions to allow bone and muscle to become stronger. Further, continuous monitoring of the research participant will be conducted by the staff for potential injuries. For example, signs of skin redness, swelling of joints, or spasticity can be indicators of injury when research participants have impaired sensation. Research participants will also be stretched by the physical therapist or trained staff member before and after each training session to prevent injury.

If any signs of risks or discomfort are noted, the experiment or training session will be immediately discontinued. If any complications arise, the stand or step training will immediately stop and [name] will immediately be informed. In addition, the research participant's primary care provider will be notified as necessary. [name] will be the medical advisor for the research participants throughout the locomotor training segment of this study. [name] or [name] will oversee all surgical related issues for the research participants.

Follow-up: After the training period has ended, patients will be followed up by Drs. [name]/[name] and [name] every three-six months for a total of three years following surgery. After three years the patients will be followed up by Drs. [name]/[name] and [name] every six months for continued long-term care until the device is explanted or the device is approved for stepping and standing in spinal cord injury. Follow-up neurological examination for the purpose of this study will be incorporated into each clinic

visit. The decision to continue to maintain the stimulators or remove them will be made during these follow-up visits.

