Stage 1A: Standing and stepping interventions

FULL ENROLLMENT CONSENT:

Stage 1B: Surgical Procedure

Stage 1C: Stimulation procedures and standing and stepping interventions

Stage 2A: Stimulation procedures and standing and stepping assessments

Stage 2B: Adaptive Multielectrode Epidural Stimulation and Locomotor Training

Stage 1A: Standing and stepping interventions

Prior to the initial surgery the participant will undergo 80 sessions of step/stand training (screening). We will evaluate the research participants with the following experiments: 1) functional neurophysiological assessment (FNPA); 2) somatosensory evoked potentials (SEP); 3) sympathetic skin responses (SSR); 4) efferent motor activity during standing; 5) efferent motor activity during stepping; 6) reflexes during supine, prone, sitting and standing before the initiation of training; 7) bladder function; 8) cardiovascular function; 9) MRI Scan; 10) Quality of life questionnaires. Each of these measurements will take between 1 and 4 hours. We will repeat these measurements at the end of the initial 80 training sessions. Participants will undergo laboratory tests to assess and reduce the risk of infectious diseases prior to surgery.

Protection against Infectious Diseases: Several lab tests (see table below) will be performed to assess the risk of infection prior to surgical implantation based on the recommendation from the Infection Prevention and Control Department (ULH) and Division of Infectious Diseases, Dept. of Medicine (UofL). [name] will oversee treatment for any positive urine culture and infections in consultation with the Division of Infectious Diseases Department.

Test	Purpose	When
Nasal swab for MRSA	To determine if colonized to decolonize and use vancomycin as pre-operative antibiotics	Approximately 4 weeks prior to scheduled surgery to allow for time for treatment, re-test + treatment and final re-test.
Peri-rectal swab for MDRO Gram-negatives	To determine if colonized and, based on organism, consider decolonization and adjustment of pre-operative antibiotics	
urinalysis urine culture	To identify infection for clearance prior to procedure	Within 30 days of scheduled surgery; may need to be repeated closer to surgery date
C-reactive protein (CRP)	To obtain for baseline measure	
Erythrocyte sedimentation rate (ESR)		
Procalcitonin		
Prealbumin/Transthyretin	To verify appropriate status for procedure	
Albumin (included in CMP)		
25-Hydroxy Vitamin D		
CBC with differential		

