Following post-surgery experiments, training will be conducted 5 times per week for 160 sessions on an outpatient basis. In Stage 2 the individuals will be seen in our laboratory on a daily basis for testing and training. After the initial 20 sessions of training, they might be asked to come train twice a day (stand and step on the same day) with a 2-4 hour resting period in between. We will evaluate the combination of epidural stimulation with manual step (locomotor) training. This stage will be conducted over four to eight months. Periodically, blood and urine samples may be collected, processed for testing as described above, and stored for batch testing at the end of the study period.

During training, the patients will be provided with epidural stimulation using the parameters defined in Stage 1.

In certain cases, the physician, [name], might recommend a specific training change or limit on sessions to mitigate risk for research participant. Any special considerations are specified in the addendum section.

The participants may be evaluated weekly for 1) efferent motor activity during standing and stepping and 2) reflexes during supine, prone, sitting and standing, as described above.

Home Training: Following the determination of optimal parameters for standing or voluntary activity, the participant might be given a Patient Programmer (Medtronic Model 37743) to translate weight bearing and stand training and/or voluntary movement with stimulation to the home environment and perform additional training. The programmer will be optimally programmed by the research team in such a way to restrict configuration changes by research participant. A pre-determined range of optimal voltages will be accessible by the research participants. A very specific protocol for stimulation and training will be given by the research team and the participant will be required to complete a training log. The research team will collect the home training log from the participant once a week and evaluate the need for changes to the home-based training protocol.

Stage 2B: Adaptive Multielectrode Epidural Stimulation and Locomotor Training

Stage 2 will evaluate the combination of our adaptive epidural stimulation strategy with manual step (locomotor) training. During training, the participants will be provided with ES using the parameters determined using the computation learning method in Phase 1.

Experimental materials.

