We will acquire lower extremity and trunk muscles surface EMG activity and kinematics bilaterally during all experimental conditions. We will also use fine-wire EMG to acquire activity from the ilio-psoas, extensor hallicus longus, extensor digitorum longus and other deep muscles muscle. We will also record individual limb loading and level of BWS during standing and stepping conditions. We may acquire continuous blood pressure with a finger cuff, breathing rate using an elastic band place loosely around their chest and temperature with 1-3 small sensors taped over their skin above and below their injury level.

Locomotor Training Intervention.

Individuals with SCI will participate in 80 sessions of weight bearing step-training (n=10) for approximately 16 - 20 weeks (60-90 minutes/session, 3-5 sessions/week) during which the individuals may be placed on the treadmill in an upright position and suspended by an overhead pulley (Innoventor, St. Louis, MO) in a harness (Robertson, Hendersen, NV). During stepping using BWST and manual assistance the maximum load will be used that avoids knee-buckling and trunk collapse [64]. A trainer positioned behind the research participant will aid in pelvis and trunk stabilization, as well as weight shifting and hip rotation, and trainers positioned at each limb will provide manual assistance using a customized technique that facilitates knee extension during stance (by manually

stimulating the patellar and Achilles' tendons) and knee flexion and toe clearance during swing (by manually stimulating the hamstrings and tibialis anterior tendons). Trainers provide assistance only when needed. Individuals will step at a normal walking speed for their height and age (0.89 m/s – 1.34 m/s) and at the maximum body weight allowed with minimal force needed by the trainers to assist during stance (4, 25). Body weight support will be continuously reduced over the course of the 80 sessions as the individuals increase their ability to bear weight on the legs during stepping. Step training sessions might progress to the overground environment when appropriate.

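### Does counting only sessions that meet an undefined progression criterion make the 80- and 160-session training totals unreliable?

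*Protocol*

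**What the plan says.** The counting rule stands once, in Section D under Locomotor Training: "The sessions will only be counted if the progression criteria is met, for example independence minutes or weight-bearing minutes". It directly follows "Participants may be asked to train twice a day; they will train both to stand and step on the same day". That part of Section D comes after the full-enrollment heading, but it opens by speaking of every participant. The rule could therefore cover all training, only the stage after implantation, or only the twice-daily sessions.

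The same text lets sessions end early: "Standing or stepping will immediately halt once the research participant feels tired or winded" and "If any signs of risks or discomfort are noted, the experiment or training session will be immediately discontinued".

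The session totals are fixed elsewhere:
- **Before implantation.** Section D (Screening) and Section G (Stage 1A) set 80 sessions. The tests are then repeated "to quantify that no motor pattern changes are achievable with locomotor training alone", and Stage 1A adds "We will repeat these measurements at the end of the initial 80 training sessions". Section G, Locomotor Training Intervention, gives this block a schedule: "for approximately 16 - 20 weeks (60-90 minutes/session, 3-5 sessions/week".
- **After implantation.** Section G (Stage 2A) says "training will be conducted 5 times per week for 160 sessions on an outpatient basis". It gives the stage four to eight months and allows twice-daily training once 20 sessions are done. Section D gives six to eight months.

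**The concern.** A total made up only of qualifying sessions is not the amount of training delivered. If qualifying depends on how well the participant performs, delivered training depends on response: a participant who seldom qualifies trains longer, or never completes the block.

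The rule can be read in two ways. Independence minutes suggest a performance test. Weight-bearing minutes suggest a minimum amount of work, which fits the early-halt rules. Under the first reading the rule sits awkwardly with a screening block that is expected to show no change in motor pattern.

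There is no concurrent control. Results are set against the best performance of earlier patients who were only trained (Section A and the end of Section G). If exposure were described only as 80 or 160 sessions, a reader could not tell how much training lay behind a good result.

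**Working it through.** **Inputs.** From Section G: 80 sessions in 16 to 20 weeks at 3 to 5 per week, 60 to 90 minutes each; 160 sessions at 5 per week over four to eight months; twice-daily training possible after 20 sessions. From Section D: six to eight months for the stage after implantation. Two assumptions are added: 365.25/12/7 = 4.348 weeks per month, and twice daily means 10 sessions per week, starting after 20/5 = 4 weeks.

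**Step 1: do the stated totals fit if every session counts?**
- 80 sessions: 16 × 5 = 80 and 20 × 4 = 80.
- 160 sessions, once daily: 160/5 = 32 weeks, and 32/4.348 = 7.4 months.
- 160 sessions, twice daily after 20: 4 + 140/10 = 18 weeks, and 18/4.348 = 4.1 months, close to the lower end in Stage 2A.

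So the totals reproduce.

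**Step 2: how much room is there for uncounted sessions?** Minimum share that must count = stated total / sessions deliverable in the window. Once daily, deliverable = 5 × weeks. Twice daily, deliverable = 20 + 10 × (weeks − 4).

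| Block and schedule | Deliverable | Minimum share counting |
|---|---|---|
| 80: 16 weeks × 5 | 80 | 100% |
| 80: 18 weeks × 5 | 90 | 89% |
| 80: 20 weeks × 5 | 100 | 80% |
| 80: 20 weeks × 4 | 80 | 100% |
| 160: once daily, 8 months (34.8 weeks) | 174 | 92% |
| 160: twice daily, 6 months (26.1 weeks) | 241 | 66% |
| 160: twice daily, 8 months (34.8 weeks) | 328 | 49% |

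Once daily, 160 sessions do not fit in 6 months (130 deliverable) or 4 months (87). Twice daily, 4 months holds about 154, just short of 160; the stated months are round figures. The windows are tight for once-daily training after implantation and at their short ends. They are loose for 20 weeks at 5 per week and for sustained twice-daily training.

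**Step 3: is a session count a measure of dose in any case?** 80 × 60 minutes = 80 hours and 80 × 90 minutes = 120 hours, a ratio of 1.5. Uncounted sessions in the 80-session block can add at most 100/80 = 1.25. The stated range of session lengths therefore moves exposure in that block more than the counting rule can within its window.

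**Step 4: does any conclusion use the count?** Section A and the end of Section G define success as performance beyond the best seen with training alone, in any individual. The number of sessions is not part of that rule. Section j plans no statistical comparison and calls the study a proof of principle without power. No session numbers are given for the historical patients, so a defined counting rule would not by itself make their exposure comparable. The repeat testing before implantation is tied to completing 80 sessions, not to a calendar date.

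**The case for a change.** The strongest case for a change is that this is an operational rule written into the protocol, not a detail of analysis. It decides when a block ends and when the next assessment falls due. The 80-session block is the within-person reference for training alone, and its results feed the decision on implantation. Without a control group, the training behind each result ought to be known. Up to 20 uncounted sessions before implantation, and up to about 168 after it in the extreme twice-daily case (328 − 160), is not trivial. One sentence would close the gap.

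Part of this stands. The term is undefined, its scope is open, and delivered sessions may exceed counted ones by amounts that differ between participants.

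The rest does not carry through to a result. Dependence of exposure on response needs the performance reading, which the text does not require. Under a minimum-work reading, which the early-halt rules suit, the rule mainly separates sessions that took place in full from those cut short. A criterion in minutes can be applied only if minutes are recorded, including for sessions that fail it, so delivered training should be recoverable; this is an inference, as the protocol does not state it. Nor does it say that uncounted sessions go unrecorded or that only completers will be reported. Participants who respond well, and so are most likely to pass the success threshold, probably count nearly every session.

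**Conclusion.** No change to the plan follows. The protocol leaves one term undefined in a ten-person pilot. At its limits, 80 counted sessions mean 80 to 100 delivered. The 160 mean 160 to about 174 once daily, or up to about 328 if optional twice-daily training were kept up to month 8. The true counted share is unknown, so these limits do not estimate what will happen. They rest on 4.348 weeks per month, on 5 times per week meaning five sessions or five training days, and on the rule applying to both blocks, which the text does not settle.

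Defining the term would change neither the success rule nor any planned comparison, and no bias in a stated direction has been shown. Analysts can fill the gap sensibly by describing delivered and counted sessions, with minutes, when they report exposure.

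Two inconsistencies in the schedule came up on the way, and neither follows from the counting rule. At 3 sessions per week, 20 weeks gives 60 sessions, and 80 would take 80/3 = 26.7 weeks. Sections D and G also give different lower limits for the stage after implantation (six and four months). Both are clerical points to reconcile when the text is next edited, and neither alters what the trial can conclude.

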[name] and the research team might ask the participant to return for training in the laboratory for extended periods of 80-200 sessions post participation in the original sessions. Training (stand or step) will be designed to optimize parameters and built to improve on previous training. During this time participants might be asked to functional train with the combination of our adaptive epidural stimulation strategy with manual locomotor training. During training, the participants will be provided with ES using the parameters determined using the computation learning method which is developed during phase 2 described below.

E. How the study population is determined and how they will be equitably recruited

There are approximately 250,000 Americans with a SCI. Of this population, 82% are male. Fifty-six percent of the injuries occur in people between the ages of 16 and 30, and the average age of an individual who has sustained a SCI is thirty-one. Thirty-eight percent of the research participants studied will be derived from a population of minorities (African-American, American Indian or Alaskan Native, Asian, Hispanic or Latino, and Native Hawaiian or other Pacific Islander). Every effort will be made to recruit women, though only about 18% of SCI patients are female. Although many people after a SCI have secondary health issues such as spasticity and frequent urinary tract infections, they are otherwise healthy individuals. Standing and stepping is considered beneficial for people with SCI who are confined to a wheelchair, as immobilization can contribute to secondary pathologies such as osteoporosis, leg muscle contractures, decreased cardiovascular health, pressure sores and muscle atrophy. Children will not be studied. Pregnant women with SCI will not be studied because the risks to the fetus are unknown. No other vulnerable research participants will be included.

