All research participants, irrespective of age or sex, will meet the following criteria: 1) stable medical condition without cardiopulmonary disease or dysautonomia that would contraindicate standing or stepping with BWST; 2) no painful musculoskeletal dysfunction, unhealed fracture, contracture, pressure sore, or urinary tract infection that might interfere with stand or step training; 3) no clinically significant depression or ongoing drug abuse; 4) no current anti-spasticity medication regimen; 5) non-progressive SCI above T10; 6) must not have received botox injections in the prior six months; 7) be unable to stand and step independently overground; 8) unable to voluntarily move all individual joints of the legs; 9) at least one-year post injury; and 10) must be at least 18 years of age. In addition, all subjects must satisfy each of the three conditions of the functional neurophysiological assessment described below.

Additionally, research participants with the following characteristics will not undergo any assessments using transcranial magnetic stimulation (TMS): 1) metal in head (except mouth) such as but not limited to cochlear implant, implanted brain stimulators, aneurysm clips; 2) increased intracranial pressure (which lowers seizure thresholds); 3) cardiac pacemakers; 4) implanted medication pumps; 5) intracardiac lines; 6) significant heart disease; 7) history of stroke or other brain lesions; 8) personal or family history of epilepsy; 9) receiving tricyclic antidepressants or neuroleptics (which lower seizure threshold); 10) heavy alcohol consumption within past 48 hours

Functional Neurophysiological Assessment (FNPA). We will use FNPA to screen potential research participants based on specific neurophysiological inclusion criteria. Participants must have no volitional control of movement below the level of the lesion, but must retain some brain influence on spinal reflexes. Our target population, which will be identified by FNPA, cannot be identified reliably using traditional assessments: hence individual subjects may be classified widely as Class A, B, or C on the ASIA SCI scale. We will include only subjects who fulfill the following three requirements:

1. There is no descending volitional control of movement below the lesion
2. Segmental reflexes remain functional below the lesion
3. Brain influence on spinal reflexes is retained

G. Design/methodology including all survey instruments, questionnaires, etc.

SCREENING CONSENT:

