CMP		
Pregnancy Test		

If a patient tests positive for MRSA, de-colonization will be recommended and monitored by the infectious disease team in collaboration with Drs. [name] and [name]. Treatment plan includes the following to be administered for 7 days: chlorhexidine gluconate (2 or 4% solution) with daily washes or a disposable impregnated cloth; mupirocin ointment (2%) applied to the nares with a cotton-tipped applicator two to three times daily. Following initial treatment, the participant will be retested for MRSA. If the participant still tests positive then treatment will include repeated decolonization as well as the following: rifampin (600 mg PO daily) plus either doxycycline (100 mg twice daily) or trimethoprim/sulfamethoxazole (one double strength twice daily). The participant will be retested following this second treatment. If the participant still tests positive then they

should be excluded from the study. The physicians will manage the medical treatment for infections and for any immediate safety concerns.

Stage 1B: Surgical Procedure

One Medtronic Specify 5-6-5 or Specify 5-6-5 SureScan MRI (Minneapolis, MN) 16-electrode epidural arrays will be implanted intraoperatively using a single surgery procedure. The surgery will be conducted at University Hospital under a combined regional and general anesthetic. General anesthesia will be utilized for part of the surgery and mild sedation for the other part. We do not anticipate that the patients will experience any pain during this operation. However, if there is any discomfort, the patients will be administered analgesics by the anesthesiologist and/or the painful area will be infiltrated with local anesthetic. Patients will be placed in the prone position with an incision made in the thoracolumbar area of the spine. We will perform a partial laminectomy at the T11–T12 interspace providing a site for electrode insertion. The incision will be approximately 2.0 – 2.5 inches. One electrode will be threaded upwards to the T11-L1 segmental levels. If necessary the second electrode will be threaded downward to the S1-S2 segmental levels for placement over the group of spinal cord nuclei where activation of the muscles occurs. Fluoroscopy and neurophysiological parameters will be used to determine the optimal lead placement that will be determined by motor system monitoring.

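### The pregnancy exclusion in Section E is missing from the Section F entry criteria and is not checked at screening, so an unrecognised pregnancy could go through about 12 to 20 weeks of training first

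*Protocol*

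**What the plan says.** Section E (study population and recruitment) gives the rule and its reason: "Pregnant women with SCI will not be studied because the risks to the fetus are unknown". The same paragraph says "Every effort will be made to recruit women, though only about 18% of SCI patients are female", so the rule applies to people the trial means to enrol.

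Section F (eligibility) opens its list with "All research participants, irrespective of age or sex, will meet the following criteria". Ten numbered items follow, the last two being "at least one-year post injury; and 10) must be at least 18 years of age", and then three conditions from the functional neurophysiological assessment. Pregnancy is in neither set.

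Section D (screening, first consent) lists a blood panel and adds that "A comprehensive drug screen by urinalysis will be done to assess the use of illicit drugs". It names no pregnancy test. It also calls for a medical history and neurological examination to settle medical eligibility, without mentioning pregnancy.

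Section G, Stage 1A, has a table of laboratory tests which "will be performed to assess the risk of infection prior to surgical implantation". One row reads "Pregnancy Test". The timing that appears to cover it is "Within 30 days of scheduled surgery; may need to be repeated closer to surgery date". Stage 1A also places the baseline evaluations, including an MRI scan, and 80 training sessions before surgery.

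**The concern.** The exclusion rests on unknown risk to the fetus, so it has to work before study exposure begins. As drafted, it stands in the recruitment narrative, while the list used to decide eligibility and the tests done at entry pass over it. The only check is tied to surgery, which comes at the end of the training-alone phase.

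The main stake is participant and fetal safety: study procedures would be given to someone the protocol says it will not study. A lesser stake is that a participant found pregnant just before implantation may be lost after completing the whole training-alone phase, in a trial planned for ten.

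**Working it through.** **Is the exclusion carried through?**

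| Place in the protocol | Pregnancy mentioned? |
|---|---|
| Section E, population | Yes, as an exclusion from being studied |
| Section F, ten entry criteria | No |
| Section F, three neurophysiological conditions | No |
| Section D, medical history and examination | Not named |
| Section D, screening blood and urine tests | No |
| Section G, Stage 1A pre-surgical table | Yes, one test |

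The neighbouring rule in Section E, that children are not studied, was carried into Section F as criterion 10 (age 18 or over). The pregnancy rule was not. Section D bases the eligibility decision on the inclusion and exclusion criteria together with the physicians' recommendation, so the gap lies in the list that matters.

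**How long from the start of training to the test?**

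Inputs:
- 80 sessions, about 16 to 20 weeks, at 3 to 5 sessions per week (Section G, Locomotor Training Intervention).
- Test within 30 days of surgery (Section G table, as it appears to read). 30 / 7 = 4.3 weeks.
- Assumption: surgery follows session 80 directly.

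1. The protocol's own duration, as sessions divided by weekly rate: 80 / 5 = 16.0 weeks and 80 / 4 = 20.0 weeks, which match the stated range. At the stated minimum rate, 80 / 3 = 26.7 weeks, which lies outside it.
2. Earliest test = training duration minus 4.3 weeks; latest test = end of training.

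| Training duration | Earliest test | Latest test |
|---|---|---|
| 16 weeks | 16 − 4.3 = 11.7 weeks | 16.0 weeks |
| 20 weeks | 20 − 4.3 = 15.7 weeks | 20.0 weeks |
| 26.7 weeks (3 per week) | 26.7 − 4.3 = 22.4 weeks | 26.7 weeks |

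3. On the stated 16 to 20 weeks, the check comes 11.7 to 20.0 weeks after training starts, or roughly 12 to 20 weeks.
4. Sensitivity to the table: the other timing entry, for the swabs, is about 4 weeks before surgery. If that applied, the earliest test would fall at 16 − 4 = 12 to 20 − 4 = 16 weeks. The conclusion does not depend on which entry governs the row.
5. The baseline evaluations come before training and so add to these figures, as does any gap between session 80 and surgery. Section D also counts only sessions that meet progression criteria, which can lengthen the course.

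**The case against.** The strongest reply is that the exclusion exists. Section E is plain, and Sections E and F do not contradict each other: one states a rule that the other does not repeat. An investigator who follows the whole protocol excludes any woman known to be pregnant, and the Section D medical history is an ordinary route by which a known pregnancy would come to light. A test is also done before implantation, anesthesia and fluoroscopy. The consent forms and the addendum the protocol mentions are not available here and could contain an entry check.

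Much of this stands. It limits the point to pregnancies not recognised at entry, and makes the consequence possible rather than certain. It does not close the gap: the protocol names no step before training that would detect such a pregnancy.

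Four stronger readings are tempting but not supported:

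- A reader might infer that following the text means admitting pregnant women. Section E says the opposite.
- A reader might infer that transcranial magnetic stimulation would be given before the test. It appears in Section F only through its own exclusions, and neither list of pre-training evaluations names it.
- A reader might take the 18% female share to mean about two of ten participants are affected. 0.18 × 10 = 1.8 is the expected number of women if the sample mirrors that share. The protocol gives no pregnancy rate.
- A reader might fault a gap of up to a month between a negative test and surgery. The timing cell for that row is broken in the text at hand, and the apparent wording foresees a later repeat.

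**Conclusion.** The point holds as a safety gap in how a stated exclusion is put into practice. Section E rules out any study of pregnant women, Section F omits the rule, and nothing named at screening checks it. An unrecognised pregnancy could pass through the baseline evaluations, the MRI scan and about 12 to 20 weeks of training first.

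That range rests on 80 sessions in 16 to 20 weeks, surgery straight afterwards, and a test no earlier than 30 days before surgery. At three sessions per week it becomes 22.4 to 26.7 weeks. How many women would be concerned cannot be estimated from the protocol. Confidence is high on the omission from Section F and on the lack of a named entry test, and moderate on the exact timing of the pre-surgical test.

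**What to change.** Reconcile Sections D, E, F and G:

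1. Add the pregnancy exclusion from Section E to the Section F list.
2. State in Section D that it is verified at the first (screening) consent, before any evaluation or training, using the urine already collected for the drug screen.
3. Keep the existing pre-surgical test and state clearly in the Section G table when it is due.

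This enforces the protocol's own rule and adds no new one. It costs a short amendment and one inexpensive extra assay per woman, with slightly more screening laboratory work. An entry test cannot detect a pregnancy that begins during training, so the pre-surgical test remains necessary and a late loss remains possible.
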